2.4.4.3 Multiplicity issues

Not Applicable.

2.4.4.4 Additional efficacy analysis(es)

Not Applicable.

2.4.5 Analyses of safety data

No formal inferential testing will be performed. Summaries will be descriptive in nature.

General common rules

All safety analyses will be performed on the safety population as defined in [Section 2.3.2](#) unless otherwise specified, using the following common rules:

- Safety analyses for the OLDFI/OLE combined periods of Cohorts 1 to 3 will be performed separately for the period pre- versus post-switch to selected Phase 3 doses.
- The baseline value for both OLDFI and OLDFI/OLE combined periods is defined as the last available value obtained up to the date and time of the first OLDFI IMP injection.
- PCSA values are defined as abnormal values considered medically important by the Sponsor according to predefined criteria/thresholds based on literature review and defined by the Sponsor for clinical laboratory tests, vital signs, and ECG (PCSA in children version dated May 2014 [[Appendix A](#)] and PCSA in adults version dated May 2014 [[Appendix B](#)], for patients who become adults during the study, ie, aged 18 years or greater during the study).
- PCSA criteria will determine which patients had at least 1 PCSA during the TEAE period, taking into account all evaluations performed during the TEAE period, including nonscheduled or repeated evaluations.
- The treatment-emergent PCSA denominator by group for a given parameter will be based on the number of patients assessed for that given parameter at least once during the TEAE period.
- All measurements, scheduled or unscheduled, fasting or not fasting, will be assigned to analysis windows defined in [Section 2.5.4](#), [Table 3](#) and [Table 4](#) in order to provide an assessment for Week 4 to Week 130 time points.
- For quantitative safety parameters based on central laboratory/reading measurements, descriptive statistics will be used to summarize results and change from baseline values by visit, using analysis windows. Summaries will also include the last on-treatment value and the worst on-treatment value. The last on-treatment value is defined as the last value

collected during the treatment period of each study period (see [Section 2.1.4](#)). The worst on-treatment value is defined as the nadir and /or the peak value during the treatment period of each study period according to the direction (minimum or maximum) of the abnormality as defined in the PCSA list.

- TEAE period stands for OLDFI TEAE period (for safety analysis of OLDFI period) or OLDFI/OLE combined TEAE period (for safety analysis of OLDFI and OLE periods combined) (see [Section 2.1.4](#)).

2.4.5.1 Analyses of adverse events

Generalities

The primary focus of AE reporting will be on TEAEs. Pre-treatment and post-treatment AEs will be described separately.

If an AE date/time of onset (occurrence, worsening, or becoming serious) is incomplete, an imputation algorithm will be used to classify the AE as pre-treatment, treatment-emergent, or post-treatment. The algorithm for imputing date/time of onset will be conservative and will classify an AE as treatment-emergent unless there is definitive information to determine it is pre-treatment or post-treatment. Details on classification of AEs with missing or partial onset dates are provided in [Section 2.5.3](#).

Adverse event incidence tables will present the number (n) and percentage (%) of patients experiencing an AE by SOC, HLGT (when applicable), HLT (when applicable), and PT. Multiple occurrences of the same event in the same patient will be counted only once in the tables within a treatment phase.

Sorting within tables ensures the same presentation for the set of all AEs within the observation period (pre-treatment, TEAE, and post-treatment). For that purpose, the table of all TEAEs presented by SOC and PT sorted by the internationally agreed SOC order and decreasing frequency of PTs within SOCs (in the cohort 4, all doses combined) will define the presentation order for all other tables by SOC and PT, unless otherwise specified. The tables of AEs by SOC, HLGT, HLT and PT will be sorted by the SOC internationally agreed order and the other levels (HLGT, HLT, PT) will be presented in alphabetical order, unless otherwise specified.

Analysis of all treatment-emergent adverse events

The following TEAE summaries will be generated:

- Overview of TEAEs, summarizing number (%) of patients with any
 - TEAE;
 - Serious TEAE;
 - TEAE leading to death;
 - TEAE leading to permanent treatment discontinuation.

- All TEAEs by primary SOC, HLT, HLT, and PT
- All TEAEs by primary SOC and PT, sorted by the internationally agreed SOC order and by decreasing incidence of PTs within each SOC (in the Cohort 3, all doses combined). This sorting order will be applied to all other tables by SOC and PT of TEAEs, unless otherwise specified;
- All TEAEs regardless of relationship and related to alirocumab according to investigator's opinion by primary SOC, HLT, HLT and PT;
- All TEAEs by maximal intensity (ie, mild, moderate or severe), presented by primary SOC and PT, sorted by the sorting order defined above;

Analysis of all treatment emergent serious adverse event(s)

- All serious TEAEs by primary SOC, HLT, HLT, and PT and by SOC/PT;
- All serious TEAEs regardless of relationship and related to alirocumab according to investigator's opinion, by primary SOC, HLT, HLT, and PT;

Analysis of all treatment-emergent adverse event(s) leading to treatment discontinuation

- All TEAEs leading to treatment discontinuation, by primary SOC, HLT, HLT, and PT and by SOC/PT;

Analysis of groupings of adverse events including selected adverse events of special interest

All grouping of TEAEs including adverse events of special interest as listed in [Section 2.1.4.1](#) will be analyzed using selections defined in [Section 2.1.4.1](#) and will be presented by SMQ/CMQ and PT (when selection is based on SMQs/CMQs) and by SOC and PT (when selection is based on the e-CRF tick box or HLT/HLT). The summaries will be sorted by decreasing incidence of PT within each SOC/SMQ (in the Cohort 3, all doses combined).

In addition, the following variables will be tabulated for the local injection site reactions TEAEs:

- Intensity of the event (mild, moderate, severe);
- Number of events divided by the number of OLDFI IMP injections , or the number of open-label injections received for the OLDFI/OLE combined period depending on the analysis period;
- Time from first OLDFI IMP injection to first injection site reaction;
- Description of the highest intensity of each symptom recorded in the specific e-CRF page;
- The use of the analgesic will be assessed with regards to the occurrence of pain;

Besides, description of symptoms and possible etiologies for General Allergic Reaction TEAE reported by investigator (using the tick box), will be presented.

Analysis of pre-treatment and post-treatment adverse events

- All pre-treatment AEs by primary SOC and PT, sorted by the internationally agreed SOC order and decreasing incidence of PTs (in the Cohort 3, all doses combined) within each SOC;
- All pre-treatment AEs leading to treatment discontinuation by primary SOC and PT, sorted by the sorting order defined above;
- All post-treatment AEs by primary SOC and PT, sorted by the internationally agreed SOC order and decreasing incidence of PTs (in the Cohort 3, all doses combined) within each SOC;
- All post-treatment SAEs by primary SOC and PT, sorted by the sorting order defined above;

Subgroup of patients with two consecutive LDL-C <50 mg/dL or two consecutive LDL-C <25 mg/dL

If applicable, similar summaries of TEAEs as those described above will be also provided on the safety subgroup population of patients with two consecutive results of calculated LDL-C <50 mg/dL (respectively calculated LDL-C <25 mg/dL) (as defined in [Section 2.1.4.7](#)). Only TEAE for which it will be confirmed or unclear that they occurred, worsened or became serious the day or after the first level of LDL-C <50 mg/dL (or LDL-C <25 mg/dL) will be considered. In case very few cases are observed, individual data listings of TEAEs will be provided on this subgroup of patients instead.

In addition, for the OLDFI/OLE combined period, the following summary tables will be provided:

- The event rate per patient year (the number of patients with an event in question divided by total patient-years) will be provided for all TEAEs by SOC and PT. For a patient with event, patient year is censored at time of first event; for patient without event, it corresponds to length of OLDFI/OLE combined TEAE period
- Kaplan-Meier curves will be provided, when appropriate, for time from first dose of OLDFI IMP to the first occurrence of selected TEAEs. Patients without any event will be censored at the end of the OLDFI/OLE combined TEAE period.

2.4.5.2 Deaths

The following summaries of deaths will be generated:

- Number (%) of patients from the safety population who died by period (on-study, on-treatment, post-study);
- TEAEs leading to death (death as an outcome on the AE as reported by the Investigator) by primary SOC, HLGT, HLT, and PT sorted by internationally agreed SOC order, with HLGT, HLT, and PT presented in alphabetical order within each SOC, for the safety population. TEAEs leading to death are TEAEs that led to death regardless of timing of

death in relation to IMP injection (ie, death occurring in the TEAE period or during the post-treatment period).

In addition deaths in included but not treated patients will be summarized.

2.4.5.3 Analyses of laboratory variables

The summary statistics (including number, mean, median, Q1, Q3, SD, minimum and maximum) of all laboratory variables (central laboratory values and changes from baseline) will be calculated for each visit or study assessment (baseline, each post-baseline value of the treatment period, last on-treatment and worst on-treatment value). This section will be organized by biological function as specified in [Section 2.1.4.3](#). For glucose, only fasting samples will be summarized.

The incidence of PCSAs (list provided in [Appendix A](#)), as well as ALT increase as defined as AESI during the TEAE period will be summarized by biological function irrespective of the baseline level and/or according to the following baseline status categories:

- Normal/missing
- Abnormal according to PCSA criterion or criteria

For parameters for which no PCSA criteria are defined for children ie, red blood cell count, albumin, monocytes and basophils, similar table(s) using the normal range could be provided.

Cortisol and ACTH

Mean changes from baseline with the corresponding SE will be tabulated by time point for cortisol during treatment period. Cortisol levels obtained at local labs will be excluded.

As the sampling time is a known confounder for the cortisol value, the timing of sample collection as well as the cortisol values by sampling time will be described graphically.

Similar table as for PCSA will be provided using the normal range. The number (%) of patients with at least one:

- Cortisol < LLN,
- Cortisol < LLN and ACTH > ULN

during TEAE period, will be presented.

Gonadal hormone assessments

Mean changes from baseline with the corresponding SE will be tabulated by time point for gonadal assessment (testosterone (boys) and estradiol (girls)) and Pituitary hormones (FSH LH) during treatment period.

Similar table as for PCSA will be provided to summarize:

- For boys: the number (%) of patients with testosterone value <LLN, testosterone value <LLN and LH >ULN, testosterone value<LLN and FSH >ULN, during the TEAE period.
- For girls: the number (%) of patients with estradiol value <LLN, estradiol value <LLN and LH >ULN, estradiol value<LLN and FSH >ULN. Separate results will be provided for girls with menstruation and without menstruation.

The descriptions above may also be performed on the subgroups of samples drawn in the morning (between 7 to 11 AM [([5](#), [6](#)]]) versus those samples drawn at times other than between 7 to 11 AM.

The correlation of calculated LDL-C with gonadal assessments during treatment period will be explored graphically in all patients combined regardless of cohort and dose, taking into account:

- The worst value of the studied parameter,
- The LDL value obtained on the same day as the worst result of the studied parameter.

This graph may also be performed taking into account samples drawn (respectively not drawn) between 7 to 11 AM.

Fat soluble vitamins (A, D, E, and K)

Mean changes from baseline with the corresponding SE will be tabulated by time point for fat soluble vitamins (A, D, E, and K) and ratio of vitamin E to calculated LDL-C, during treatment period.

Similar table as for PCSA will be provided using the normal range. This table will summarize the number (%) of patients with value < LLN during the TEAE period (except for ratio of vitamin E to calculated LDL-C).

The correlation of calculated LDL-C with fat soluble vitamins (A, D, E, and K) during the treatment period will be explored graphically in all patients combined regardless of cohort and dose, taking into account:

- The worst value of the studied parameter,
- The LDL value obtained on the same day as the worst result of the studied parameter.

Drug-induced liver injury

The liver function tests, namely AST, ALT, ALP, and total bilirubin, are used to assess possible drug-induced liver toxicity. The proportion of patients with PCSA values or ALT increase as defined in AESI section (see [Section 2.1.4.1](#)) during TEAE period by baseline status will be displayed for each parameter.

An evaluation of drug-induced serious hepatotoxicity (eDISH) with the graph of distribution of peak values of ALT versus peak values of total bilirubin will also be presented using post-baseline values during TEAE period. Note that the ALT and total bilirubin values are presented on a

logarithmic scale. The graph will be divided into 4 quadrants with a vertical line corresponding to 3 x ULN for ALT and a horizontal line corresponding to 2 x ULN for total bilirubin.

Listing of possible Hy's law cases identified (ie, patients with any elevated ALT>3 x ULN, and associated with an increase in bilirubin >2 x ULN, concomitantly or not) with ALT, AST, ALP, total bilirubin, and if available direct and indirect bilirubin will be provided.

The incidence of liver-related TEAEs will be summarized. The selection of PTs will be based on SMQ Hepatic disorder (see [Section 2.1.4.1](#)).

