- Cohort 4 will receive second alirocumab allocation and administration for OLE phase.
- Check of stability of background LMT.
- IVRS/IWRS contact to get treatment kit number for 1 kit resupply.
- Obtain fasting blood sample for:
 - Lipids: total-C, calculated LDL-C, HDL-C, TG, non-HDL-C, Apo B, Apo A-1, ratio Apo B/Apo A-1, and Lp(a) for Cohorts 1 to 3.
 - Lipids: total-C, calculated LDL-C, HDL-C, TG, non-HDL-C for Cohort 4.
 - Liver panel (ALT, AST, ALP, and total bilirubin),
 - Hematology: red blood cell count including hematocrit, hemoglobin, WBC count with differential count and platelets,
 - Chemistry: glucose, sodium, potassium, chloride, bicarbonate, calcium, phosphorous, urea nitrogen, creatinine, uric acid, total protein, LDH, albumin, and γ GT,
 - CPK,
 - Anti-alirocumab antibodies,
 - Adrenal gland hormones: cortisol (with reflexive ACTH levels if cortisol <LLN), dehydroepiandrosterone sulfate (DHEAS),
 - Gonadal and pituitary hormones: testosterone (male) and estradiol (female), luteinizing hormone (LH), follicle-stimulating hormone (FSH),
 - Fat soluble vitamins: retinol (vitamin A), 25hydroxy-vitamin D (vitamin D), alpha-tocopherol (vitamin E), phylloquinone (vitamin K).
- Reminders:
 - An appointment will be given for the next study site visit,
 - Remind patient to be in fasting conditions (ie, overnight, at least 8 hours fast and refrain from smoking) for next study site visit. Also, alcohol consumption within 48 hours and intense physical exercise within 24 hours preceding the next study site visit are discouraged,
 - Patient to bring the diary, and used and unused kits at the next study site visit.

10.1.4.5 Visits 12, 14, 16, 18 (every 24 weeks)/ Visit 12 only for Cohort 4

- Collect AEs.
- Record concomitant medication.
- Perform physical examination.
- Get body weight and height measurements.
- Get Tanner stage measurement by the same investigator/designee at each visit if possible.

- Take vital signs including HR and BP.
- Urine pregnancy test (females who have experienced menarche only).
- Review patient's diet. Patient should be on a diet in accordance with the American Academy of Pediatrics guidelines (1) or equivalent.
- If the prefilled syringe becomes available: Data collection on alirocumab administration and alirocumab compliance check by review of diary and treatment kit accountability.
- Check of stability of background LMT.
- IVRS/IWRS contact to get treatment kit number for 1 kit resupply.

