2.4.5.6 Tanner stages measurement

Boys—development of external genitalia, girls—breast development, boys/girls—pubic hair stages as well as a global tanner puberty evaluation (Prepubescent, Pubescent and Postpubescent) will be described using count and percentage.

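### Hormone summaries ignore pubertal stage and Tanner stage is reported only as counts, so normal puberty can mask hormone suppression in the planned mean changes and confound the LDL-C plots

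*SAP*

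**What the plan says.** **Mean changes.** SAP 2.4.5.3 says: "Mean changes from baseline with the corresponding SE will be tabulated by time point for gonadal assessment (testosterone (boys) and estradiol (girls". LH and FSH are in the same sentence, with no split by sex stated. SAP 2.4 presents results by cohort and by dose group within cohort. SAP 2.4.5 fixes baseline at the last value before the first main-phase injection and keeps it for the combined main and extension period.

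**Low values.** For boys the SAP counts "the number (%) of patients with testosterone value <LLN, testosterone value <LLN and LH >ULN", and the same with FSH. Girls have the matching table for estradiol, and "Separate results will be provided for girls with menstruation and without menstruation". These tables follow the format for potentially clinically significant abnormalities, which are shown "irrespective of the baseline level and/or according to the following baseline status categories".

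**LDL-C plots.** "The correlation of calculated LDL-C with gonadal assessments during treatment period will be explored graphically in all patients combined regardless of cohort and dose". Each point pairs a worst hormone value with the LDL-C from the same day.

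**All laboratory variables.** SAP 2.4.5.3 also gives medians, quartiles, SD, range and last and worst on-treatment values.

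**Tanner stage.** SAP 2.4.5.6 reports the sex-specific components, and a "global tanner puberty evaluation (Prepubescent, Pubescent and Postpubescent) will be described using count and percentage".

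**Extension visits.** Protocol 10.1.4 schedules hormones at Visits 11, 13, 15, 17 and 19. At Visits 12, 14, 16 and 18 it says "Get Tanner stage measurement by the same investigator/designee at each visit if possible". Both are done at the end-of-extension visit.

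**The concern.** Children enter at Tanner 1 (ages 8 to 9) or at Tanner 2 or above (ages 10 to 17), and the study has no control arm. Pubertal stage and each child's own progression are therefore the natural yardsticks for a hormone change. Neither enters the hormone tables, apart from menstruation status in girls.

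Three things are at stake:

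- A drug effect that slows a pubertal rise can appear in a mean-change table as a normal increase.
- A pooled plot of hormone against LDL-C can show a relation that reflects only differences in maturity between children, or can hide a real one.
- Slowed pubertal progression is hard to read from counts per visit when the set of children changes between visits.

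The SAP accepts the principle elsewhere. It treats sampling time as a confounder for cortisol, allows hormone results to be split by morning and other samples, and separates girls by menstruation. It does not use the direct maturity measure that the study collects.

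**Working it through.** The documents give no power or precision figure for hormones, so there is nothing to reproduce. The check sets the outputs side by side and adds simple arithmetic.

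**1. Where maturity enters**

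| Output (SAP 2.4.5.3, 2.4.5.6) | Split by sex | Maturity |
|---|---|---|
| Mean change, testosterone and estradiol | By definition | None |
| Mean change, LH and FSH | Not stated | None |
| Testosterone or estradiol <LLN, alone or with LH or FSH >ULN | Yes | Menstruation (girls); none (boys) |
| LH or FSH <LLN | Not tabulated | - |
| Worst hormone value against LDL-C | Not stated | None |
| Tanner stage | Components are sex-specific | Counts; no stated shift |

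**2. Masking in the mean change.** Let R be the level puberty alone would give relative to baseline, and f the fraction suppressed. The net change is R(1 - f) - 1. It stays at or above zero until f exceeds 1 - 1/R. R is an assumption.

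| R | Suppression needed before the change turns negative |
|---|---|
| 1.5 | 33% |
| 2 | 50% |
| 5 | 80% |
| 10 | 90% |

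For example, R = 2 and f = 0.25 gives 2 x 0.75 - 1 = +50%.

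**3. Time for R to grow.** Main-phase hormones run from Week 0 to Week 8, so the problem lies mainly in the extension. Protocol 6.2.1 gives a maximum of about 24 months for the first patients in Cohorts 1-3 and about 7 months for Cohort 4. For Cohorts 1-3, SAP 2.4 cuts the combined analysis by assigned dose group at the switch to Phase 3 doses.

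**4. LDL-C plots.** SAP 2.4.5 defines worst as the nadir or peak during treatment, so each child supplies his or her own value. If low is the abnormal direction, as the <LLN tables imply, less mature children would tend to supply lower points regardless of LDL-C. Maturity can also be related to LDL-C, because dose is set by weight. In Cohort 3 (Protocol section 4) mean LDL-C change was -17.5% below 50 kg and +4.0% at 50 kg or above.

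**5. Which cells are usable.** This takes 40 planned patients, 8 dose groups, and an even spread over sex and category (assumed).

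| Cells | Patients per cell |
|---|---|
| Dose group | 40/8 = 5.0 |
| Dose x sex | 40/16 = 2.5 |
| Dose x sex x three puberty categories | 40/48 = 0.83 |
| Sex x five Tanner stages, pooled over doses | 40/10 = 4.0 |
| Sex x three puberty categories, pooled over doses | 40/6 = 6.7 |

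If each sex is equally likely, a dose group of 4, 5 or 6 has at most one child of a given sex with probability 5/16 = 31%, 6/32 = 19% or 7/64 = 11%. No SE can then be computed, so pooling over doses gives up little.

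**6. Visit alignment (Protocol 1.4).** In Cohorts 1 and 2, hormones fall at Weeks 28, 52, 76, 100 and 124, and Tanner at Weeks 16, 40, 64, 88 and 112. Week 28 is 12 weeks from both Week 16 and Week 40, so a nearest-assessment rule needs a tie-break. Cohort 3 also alternates, mostly 12 weeks apart. In Cohort 4, the Week 24 hormones lie 12 weeks from the Week 12 and Week 36 Tanner assessments. The two coincide only at the end of the extension. SAP 2.1.4.3 does list Visit 8 in its general list of extension laboratory visits, but the Protocol flow charts schedule no hormones there. In the main phase, the Week 8 hormones have no same-visit Tanner assessment.

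**The case against.** The strongest reply is that the mean change is only one of several outputs. Patient-level counts of low testosterone or estradiol, alone or with raised LH or FSH, are not hidden by a rising group mean. If the laboratory's limits are age- or stage-specific, those counts already adjust for maturity in both sexes. The laboratory manual and the SAP's pediatric abnormality list are not in the available text. This stands as a real mitigation, but a conditional one: nothing available states the basis of the ranges. The counts also omit low LH or FSH, so a central pattern of suppression is not tabulated.

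Second, the weight-defined dose groups are already a crude maturity split. That is partly right. But one cut at 50 kg does not follow a child through puberty, and it ties maturity to dose.

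Third, the LDL-C plots are exploratory and no inferential testing is planned. That limits the harm. A reader might also infer that prepubertal children are picked out as the worst cases. The definition does not support that, since every child contributes an individual nadir or peak. What remains is confounding between children.

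Fourth, reporting counts and percentages does not rule out a shift table, and clinically significant examination findings are reported as adverse events. So it would be too strong to say that delayed puberty cannot be seen. The narrower point is that no change from screening is specified.

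**Conclusion.** The point holds as a moderate gap in descriptive safety outputs that is cheap to close. No hormone output uses Tanner stage, boys have no maturity split at all, low LH and FSH are not counted, and Tanner progression is not specified as an analysis. Without a control arm, pubertal rises can mask suppression in the mean changes, by amounts that depend on the assumed R (33% for R = 1.5, 80% for R = 5). Maturity can also confound the pooled LDL-C plots.

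A reader might infer that the study cannot distinguish suppression from normal puberty at all. The documents do not support that. Low gonadal hormone with high LH or FSH could flag a primary gonadal problem if the ranges suit the child's age or stage. A reader might also take 24 months to apply to every hormone table. It is a maximum for the first Cohort 1-3 patients; Cohort 4 has about 7 months and the main phase 8 weeks.

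The conclusion rests on the available text not stating age- or stage-specific limits. The cell sizes assume an even spread. Actual cells will be unequal, since Tanner 1 at entry is confined to ages 8 to 9.

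**What to change.** Change the SAP only, using data the Protocol already collects:

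- Add summaries of testosterone, estradiol, LH and FSH pooled over doses, by sex and the three-level puberty category already named in SAP 2.4.5.6. Use the Tanner assessment nearest each sample, with a stated tie-break, and add individual patient profiles.
- Add a Tanner shift table from screening, by sex.
- Show the LDL-C plots by sex, with puberty category marked.
- Add counts of LH <LLN and FSH <LLN.
- Apply age- or stage-specific reference ranges where the laboratory provides them, and state which ranges are used.
- Reconcile the Visit 8 entry in SAP 2.1.4.3 with the Protocol flow charts.

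The cost is a few more descriptive tables and figures, with cells averaging about 6 to 7 patients before attrition. Five Tanner stages by sex would average only 4.0 per cell, so the three-level category is preferable. Assessing Tanner at the hormone visits would improve the match but needs a protocol amendment. It is optional and not required for this fix.

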10.6.2.2 Acute allergic injection reactions

Acute allergic injection reaction (which are considered under the category of general allergic drug reactions) is defined as any adverse event that occurs during or shortly after injection of the IMP (characterized by but not limited to hypotension, bronchoconstriction, urticaria, edema, angioedema, nausea, vomiting). Emergency equipment and medication for the treatment of these potential adverse effects (eg, antihistamines, bronchodilators, IV saline, corticosteroids, acetaminophen, and epinephrine) must be available for immediate use for the injections at the site visits.

Patients will be observed at the investigational site for at least 30 minutes following the injection that takes place at the inclusion visit. Patients should be treated symptomatically if any AEs are observed. Patients are to remain at the site until any acute injection reaction is assessed as stable, per the Investigator's discretion. General Allergic Reaction and/or Local Injection Site Reaction Complementary Form will have to be completed.

10.6.3 Recommendations for managing and monitoring patients with very low LDL-C levels (ie, LDL-C<50 mg/dL [1.30 mmol/L]) during the OLE period

If a patient achieves a very low LDL-C level (ie, LDL-C<50mg/dL [1.30 mmol/L] on one or more occasion) during the OLE period, then the Investigator will:

- Call the patient / parent as soon as possible to inquire about interval occurrence of AEs, particularly any AEs related to visual problems.
- Decide whether the patient should be requested to rapidly have an unscheduled site visit, or assessment could be done at the next scheduled visit.
- At the site visit, plan for the following, based on Investigator's medical judgment:
 - Assess the need to have blood drawn from the patient for a repeat lipid assessment in order to confirm the observation of very low LDL-C,
 - Assess the need for conducting clinical investigations, arranging specialist consultation(s) as needed, including with an eye specialist in case of visual problems, as needed, and any relevant additional work-up,

- Assess the need for alirocumab treatment temporary or permanent discontinuation, or continuation. Regardless of the action taken regarding alirocumab treatment, the patient should continue the study,

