- Assess the need to have blood drawn from the patient for adrenal gland hormones, gonadal hormones, pituitary hormones, and fat soluble vitamins if not planned per protocol at this visit.

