2.5.5 Unscheduled visits

For all parameters, unscheduled visit measurements may be used to provide a measurement for a time point, a baseline, a last or a worst value, if appropriate according to their definitions. The measurements may also be used to determine abnormal/PCSA.

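### Extra vitamin and hormone samples drawn after a low LDL-C in the extension can supply the worst value plotted against LDL-C, so a small to moderate association can arise without any true effect

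*SAP*

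**What the plan says.** **Protocol 10.6.3** applies in the open-label extension, where lipid results go to the investigator (Protocol 6.1, 8.3.2): "If a patient achieves a very low LDL-C level (ie, LDL-C<50mg/dL [1.30 mmol/L] on one or more occasion) during the OLE period". The investigator is then to do three things.
- Telephone the family: "Call the patient / parent as soon as possible to inquire about interval occurrence of AEs, particularly any AEs related to visual problems". This step carries no condition.
- Decide whether an unscheduled visit is needed.
- At the site visit, consider further work: "At the site visit, plan for the following, based on Investigator's medical judgment". The list includes a repeat lipid sample and this item: "Assess the need to have blood drawn from the patient for adrenal gland hormones, gonadal hormones, pituitary hormones, and fat soluble vitamins", where these are not already planned at that visit.

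No corresponding step is given for patients who stay at 50 mg/dL or above.

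**Scheduled sampling.** In the extension, vitamins and hormones are drawn every 24 weeks (Visits 11, 13 and so on) and at the end of the period. Lipids are also drawn at the visits between (Protocol 10.1.4.4 to 10.1.4.6). A low LDL-C can therefore appear at a visit with no vitamin or hormone draw.

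**SAP.** Section 2.4.5.3 states: "The correlation of calculated LDL-C with fat soluble vitamins (A, D, E, and K) during the treatment period will be explored graphically". It uses the worst value of the parameter and the LDL-C of the same day, in all patients regardless of cohort and dose. Gonadal assessments have the same plot. Section 2.4.5 defines the worst value as the nadir or peak over the treatment period of the study period concerned. Section 2.5.5 adds that "unscheduled visit measurements may be used to provide a measurement for a time point, a baseline, a last or a worst value". Section 2.4 asks for results for the dose-finding period alone and for the dose-finding and extension periods combined.

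**The concern.** The number of draws that can supply a patient's worst value depends on that patient's LDL-C. A minimum taken over more draws is lower on average, even if the vitamin or hormone has nothing to do with LDL-C. The extra draws fall in patients whose LDL-C is low, so the more extreme minima are paired with low LDL-C values. The plot can then lean in the direction it is meant to explore (low LDL-C with low vitamin or hormone), and neither document flags or separates the samples that came from the trigger.

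About 40 patients are planned and there is no control arm against which to calibrate the pattern. A pattern of this kind could raise a false concern, or leave a real one hard to interpret. The SAP already shows care about sampling elsewhere: it treats time of day as a confounder for cortisol and allows the gonadal plots to be split by draw time.

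**Working it through.** The documents give no figure for this association, so there is none to reproduce. The check asks how large it can be when no true effect exists.

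**1. How often the trigger could fire.** The minimum eligible LDL-C is 130 mg/dL. Falling below 50 from there needs a reduction of 1 − 50/130 = 61.5%. The largest mean change reported in Protocol section 4 is −46.1% (Cohort 2), which takes 130 to 130 × 0.539 = 70 mg/dL. Assume the percent change is normal with SD 15 to 25 points (not in the documents). The chance of a value below 50 at one visit is then 15–27% from a baseline of 130, 7–18% from 160 and 3–14% from 190.

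**2. Why extra draws matter.** For independent draws, each with a 2.5% chance of an abnormal value, P(at least one abnormal) = 1 − 0.975^k.
- Six draws: 14.1%. With 1, 2 or 4 more: 16.2%, 18.3%, 22.4%.
- Three draws (Cohort 4: Weeks 8, 24, 48): 7.3%. With 1, 2 or 4 more: 9.6%, 11.9%, 16.2%.

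At a within-patient correlation of 0.5, the expected minimum in SD units is −0.90 for 6 draws, −0.95 for 7, −1.01 for 8 and −1.09 for 10.

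**3. Null simulation of the SAP plot.** There were 40 patients and 800 runs, with the vitamin or hormone independent of LDL-C. Each patient had 6 scheduled draws with LDL-C and 4 LDL-C-only visits. After each LDL-C below 50, one further draw with same-day LDL-C was taken with probability 0.5 or 1. Assumed: between-patient SD of LDL-C 25 and within-patient SD 15 mg/dL; within-patient correlation of the vitamin or hormone 0.5 or 0. The result is the mean Spearman correlation of the worst (lowest) value with same-day LDL-C. A positive value means that low goes with low.

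| Mean on-treatment LDL-C (mg/dL) | Ever <50 | Corr. 0.5, half drawn | Corr. 0.5, all drawn | Independent, half drawn | Independent, all drawn |
|---|---|---|---|---|---|
| 110 | about 8% | 0.011 | 0.021 | 0.024 | 0.036 |
| 90 | about 26% | 0.030 | 0.055 | 0.060 | 0.102 |
| 70 | about 55% | 0.058 | 0.117 | 0.120 | 0.205 |

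Under the Cohort 2 mean effect these three levels correspond to baselines of 110/0.539 = 204, 90/0.539 = 167 and 70/0.539 = 130 mg/dL. The bottom row therefore puts the average patient at the eligibility floor with the best effect reported so far.

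**4. Same simulation, scheduled draws only.** The mean correlation lies between −0.009 and 0.001 in all six scenarios. The artefact comes from the triggered draws and disappears without them.

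**5. Direction of error in the check.** The simulation lets the trigger act after all ten visits and always supplies a same-day LDL-C. In the trial the Week 8 visit is masked and the repeat lipid sample is optional. The figures therefore lean high.

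**The case against.** The strongest reply is that the effect is small and conditional. The extra draws are at the investigator's judgment and the protocol does not require them. A triggered value reaches the plot only if LDL-C is drawn that day, which is also discretionary. Combined-period safety analyses for Cohorts 1 to 3 are split at the switch to the Phase 3 doses (SAP 2.4, 2.4.5), which shortens the window over which draws accumulate. Vitamins and hormones are also tabulated as mean change by time point, with one value per window, and those tables do not use the worst of many draws. For scale, the sampling SD of a rank correlation with 40 patients under the null is about 1/√39 = 0.16, larger than most entries in the table. Allowing unscheduled values into worst-case safety displays is also a deliberate convention.

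All of this limits the size, and it stands. It does not remove the mechanism. The shift runs in one direction, and the same triggered visits can feed several of the vitamin and hormone plots at once. Descriptive status is limited protection for a display whose purpose is to show a correlation.

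Four stronger readings are tempting, and the documents do not support them.
- *The trigger obliges extra sampling.* Only the telephone inquiry is unconditional.
- *The plan is bound to produce a low-LDL-C signal.* A much larger null correlation (0.37) appears if low-LDL-C patients have 6 draws and the others 1. That contrast reflects time on study, and nothing shows that longer follow-up goes with lower LDL-C.
- *The adverse event subgroup is inflated in the same way.* SAP 2.4.5.1 says "similar summaries of TEAEs as those described above will be also provided on the safety subgroup population of patients with two consecutive results", but it names no comparison group. It requires two low values at least 21 days apart (SAP 2.1.4.7), whereas the call needs one, and it discards events before the first low value. Adverse events are also collected from everyone at each extension visit, so the call may only bring reports forward.
- *Dose-finding results are affected.* Sites are masked to lipids then, and Protocol 10.6.3 applies only in the extension.

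**Conclusion.** The concern holds for the LDL-C plots of vitamins and gonadal assessments in the combined period. Triggered samples can create a small to moderate positive association with no true effect. The null correlation is about 0.01 to 0.12 at a within-patient correlation of 0.5, and up to about 0.2 with independent values and a draw after every trigger. These sizes rest on assumed LDL-C levels and variances, an assumed share of triggers followed by a draw, and same-day LDL-C each time; the documents supply none of these. Adrenal hormones are outside the point because the SAP plans no LDL-C plot for them. The low-LDL-C adverse event summaries need only a note on how events are ascertained. The change is worth making because it is cheap and removes the artefact, not because a large distortion is expected.

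**What to change.** In SAP 2.4.5.3, for the combined dose-finding and extension period:
- base the plots of LDL-C against vitamins and against gonadal assessments on same-day pairs from protocol-scheduled samples;
- show unscheduled samples drawn under Protocol 10.6.3 with a separate symbol or in a listing;
- keep all samples, scheduled or not, in the counts of patients below the lower limit of normal, so that no safety information is lost.

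In SAP 2.4.5.1, add one sentence to the low-LDL-C subgroup: after a low value in the extension, ascertainment of adverse events includes an active inquiry. Tables with and without events first reported at such a contact are not requested, because the documents do not show that those events can be identified. No separate presentation of the masked period is needed either, since SAP 2.4 already provides it.

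The cost is SAP wording and a plotting flag, with no change to patient care. The downside is fewer points per patient in the plots.
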